Patients will undergo dynamic, first pass, stress perfusion imaging during maximal hyperemia induced with Lexiscan™. Imaging will commence approximately 90 seconds after a bolus of Lexiscan™ (0.4 mg per each 5 mL injection). The Lexiscan™ is followed immediately by a bolus of 10 cc saline. In order to achieve the correct timing of the dynamic image acquisition, contrast administration will begin approximately 80 seconds after the Lexiscan™ bolus to allow the contrast to reach the heart at the moment of maximal hyperemia. Data will be acquired for 30 seconds with both X-ray tubes set at 80 – 100 kV, a gantry rotation time of 0.28 seconds, and a tube current of 300 mAs per rotation. Temporal resolution is approximately 75 ms. Patients will be instructed to hold their breath for the first 15 seconds of the scan, as this is the most important portion of the data acquisition for quantifying myocardial blood flow. They will then be instructed to breath shallowly for the remaining 15 seconds. Perfusion imaging is performed in an ECG-triggered shuttle mode in which the table shifts between two z-positions of the heart to allow coverage of nearly the entire left ventricle. End systolic imaging is used to reduce motion artifacts, to image the heart at its smallest dimensions, and to reduce beam-hardening artifacts from contrast in the LV cavity. The relatively fast rotation time combined with the dual source system gives markedly improved temporal resolution, which helps to reduce motion artifacts associated with the rise in heart rate that frequently occurs after Lexiscan™ administration. With a detector width of 38 mm and 10% overlap between the two imaging positions, the coverage of the acquisition is 73 mm. In some patients, small portions of the base or apex could be cut off. A total of 14 or 15 image volumes during myocardial passage of the contrast bolus will be acquired. CT MPI studies will use 40 – 50 mL of contrast agent (Ultravist 370) administered at a flow rate of 4 – 6 mL/s. Following the perfusion imaging, the Lexiscan™ will be

reversed with 1 mg/kg of aminophylline per standard clinical protocol if indicated by the supervising physician.

CT Perfusion Data Reconstruction and Analysis:

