We will present comparisons of normal or abnormal perfusion determined from SPECT/MRI stress perfusion imaging or CT perfusion using the standard 17-segment model. We will also present a comparison of ischemia by CT perfusion (based on vascular territory) compared to anatomic evidence of significant CAD at catheterization. Any segments cut off by the limited z-axis scan range on perfusion CT will be excluded. Given 30 patients, we will have a maximum of 510 regions available to compare CT perfusion and SPECT/MRI stress perfusion. We will first perform a binary analysis where each segment is classified as either normal or abnormal, since the relative severity of perfusion defects has not been defined for CT. If feasible based on the number of patients with SPECT/MRI stress perfusion scans, we will compare the number of abnormal segments in each patient by each methodology using a kappa statistic. We will also use standard SPECT/MRI stress perfusion grading of perfusion (1 – 4 scale) and a similar scale for CT perfusion defect severity (also 1 – 4) based on prior measurements of absolute myocardial perfusion (ml/100 ml/min) with each segment graded as 1, 2, 3 or > 4 standard deviations from the norm. We will then perform linear regression (Pearson's correlation) to derive R values for CT perfusion versus SPECT/MRI stress perfusion imaging perfusion grade for each segment.

E. PROTECTION OF HUMAN SUBJECTS

E.1 RISK TO THE SUBJECTS

E.1.a Human Subject Involvement and Characteristics

This study will include 100 adults who present to the MUSC ED, hospital, or outpatient clinic with a clinical history and symptoms suspicious for cardiac ischemia and who have undergone or will likely undergo nuclear stress testing (SPECT).

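### D.2 makes no allowance for correlation among segments of one heart, so a standard 95% CI for CT versus SPECT/MRI segment agreement may be too narrow

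*Combined protocol and SAP*

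**What the plan says.** D.2 (Statistical Methods / Sample Size Justification) compares CT perfusion with SPECT or MRI on the 17-segment model and sizes the comparison in segments: "Given 30 patients, we will have a maximum of 510 regions available to compare CT perfusion and SPECT/MRI stress perfusion". The first step is at segment level: "We will first perform a binary analysis where each segment is classified as either normal or abnormal". If there are enough comparator scans, "we will compare the number of abnormal segments in each patient by each methodology using a kappa statistic"; no weighting is given. A linear regression on 1–4 severity grades then serves "to derive R values for CT perfusion versus SPECT/MRI stress perfusion imaging perfusion grade for each segment".

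The number of segments per patient will vary: "Any segments cut off by the limited z-axis scan range on perfusion CT will be excluded". D.1 (CT myocardial perfusion protocols) explains why: "In some patients, small portions of the base or apex could be cut off".

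Earlier in D.2, a general rule attaches 95% confidence intervals to rates and sets significance at P of 0.05 or less. It is not repeated for the segment comparison. No section mentions clustering, within-patient correlation, a design effect or a method that would deal with them.

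Section A promises findings per patient and per segment and rules out a preplanned comparison of diagnostic accuracy. Sections A and D.2 both say the comparative data are meant to help plan later, adequately powered studies.

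**The concern.** Segments of one heart are not separate experiments. According to D.1, they share one contrast bolus, one hyperaemic response, one breath-hold, and one patient-level motion correction and arterial input function. A poor scan or a mistimed bolus can spoil agreement in many segments at once. That is an inference; the documents give no figure for it.

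The plan's general rule asks for an interval on rates, and the only denominator it offers for this comparison is 510. With no further instruction, the usual choice is a binomial interval on segments. If agreement clusters by patient, that interval overstates how precisely agreement is known. The same applies to a P value or interval for a correlation pooled over segments. Planning later trials needs both the precision of agreement and the within-patient correlation; an unclustered analysis misstates the first and leaves the second unreported.

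The count kappa raises a related problem. It reduces each patient to a number of abnormal segments, so it discards location, and without weights it penalises a one-segment difference as heavily as a ten-segment one.

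**Working it through.** **Inputs from D.2:** 30 patients; 17 segments each; 95% confidence level. **Assumed, because the documents give neither:** segment agreement p = 0.80; ICC of agreement within patients from 0 to 0.3.

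**The plan's figure.** 30 × 17 = 510, which reproduces exactly. It is an upper limit: every patient needs a SPECT or MRI comparator and no segment may be cut off.

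**Interval for segment agreement.** Design effect DE = 1 + (17 − 1) × ICC; effective n = 510 / DE; half-width = 1.96 × √(p(1 − p) / effective n). With no clustering this is 1.96 × √(0.8 × 0.2 / 510) = 3.47 points. The last column is the coverage of the unclustered 95% interval in a beta-binomial simulation (30 patients, 40,000 runs).

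| ICC | DE | Effective n | Half-width (points) | Coverage of unclustered CI |
|---|---|---|---|---|
| 0 | 1.00 | 510 | 3.5 | 95% |
| 0.02 | 1.32 | 386 | 4.0 | 91% |
| 0.05 | 1.80 | 283 | 4.7 | 85% |
| 0.10 | 2.60 | 196 | 5.6 | 77% |
| 0.20 | 4.20 | 121 | 7.1 | 65% |
| 0.30 | 5.80 | 88 | 8.4 | 58% |

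Mean estimated agreement was 0.80 throughout, so the point estimate is not affected. The ratio of widths is √DE and does not depend on p. At ICC 0.3 the half-width goes from 4.0 to 9.6 points for p = 0.70, and from 2.6 to 6.3 for p = 0.90.

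Cut-off segments change little. If all 30 patients lost the apex (assumed), 480 segments remain, and the half-width is 4.7 (ICC 0.05) to 8.4 (0.3) against 3.6 unclustered.

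**How small the effect could be.** Suppose abnormal-segment counts of 0 to 5, five patients each, and independent disagreement of 10% in normal and 30% in abnormal segments (all assumed).

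- Variance of the counts: 2.92. Between-patient variance of the number of agreeing segments: (0.30 − 0.10)² × 2.92 = 0.117.
- Within-patient variance: 14.5 × 0.09 + 2.5 × 0.21 = 1.83. Total: 1.947.
- Mean agreement: (14.5 × 0.9 + 2.5 × 0.7) / 17 = 0.871. Binomial variance: 17 × 0.871 × 0.129 = 1.915.
- DE = 1.947 / 1.915 ≈ 1.02, so the interval widens by under 1%.

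Defects that cluster by patient therefore do not by themselves make disagreement cluster.

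**Segment kappa.** In a latent-normal simulation (30 × 17, 20% abnormal), clustering raised the standard error by 1% to 29%, depending on how strongly defects and reading errors were shared within a patient.

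**Correlation R.** At an assumed R = 0.60, Fisher's z gives 0.54 to 0.65 on 510 independent segments. With DE 5.8 as a rough guide it gives 0.45 to 0.72. For a single segment position in 30 patients it gives 0.31 to 0.79, with no clustering involved.

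**Count kappa.** These are constructed examples with the same 30 patients, who have 75 abnormal segments.

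- CT calls one extra segment in every patient. Count kappa is −0.16 unweighted, 0.53 with linear weights and 0.85 with quadratic weights; segment kappa is 0.80.
- Counts are identical but only 35 of the 75 abnormal segments coincide. Count kappa is 1.00. Segment agreement is (510 − 80) / 510 = 0.843, chance agreement is (75² + 435²) / 510² = 0.749, and segment kappa is (0.843 − 0.749) / (1 − 0.749) = 0.37.

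**The case against.** The strongest reply is that D.2 makes no wrong statement. It attaches no interval, standard error or test to the 510 segments and calls the number a maximum. A reader might infer that the plan commits to treating 510 segments as independent; it does not, and the point is a gap in the method. This stands.

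The reply also holds for parts of the analysis. A kappa on per-patient counts uses one value per patient, and a correlation at each segment position uses one segment per patient, so clustering does not touch either. Because the kappa sentence follows the segment classification, a segment kappa may have been intended. In that case clustering does matter, though by an uncertain amount.

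The size is assumed. The relevant ICC is that of agreement between modalities, and the example with a design effect of 1.02 shows it could be negligible. A flat statement that the intervals will be too narrow is therefore not supported.

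Three neighbouring points might look like further errors but carry little weight:

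- D.2 also plans "a comparison of ischemia by CT perfusion (based on vascular territory) compared to anatomic evidence of significant CAD at catheterization". With the 15 catheterised patients that D.2 anticipates and three territories each (assumed), the half-width at 80% is 12.3 to 14.8 points for ICC 0.05 to 0.3, against 11.7 unclustered.
- The CT grades are worded "with each segment graded as 1, 2, 3 or > 4 standard deviations from the norm". A reader might infer that 3 to 4 SD is left ungraded, but if the numbers are lower limits the bins are contiguous. This needs only clearer wording.
- R on grades shows association and not agreement, but the plan does not claim otherwise.

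What does not stand is that nothing needs changing. The CI rule covers rates, the per-segment comparison is promised, and nothing steers the analyst away from a binomial interval on segments.

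**Conclusion.** The concern holds in conditional form. If agreement is positively correlated within patients, a standard binomial interval on segment agreement, or inference on a pooled R, would be too narrow. Over the assumed ICC range of 0.02 to 0.3, the correct interval is about 1.15 to 2.4 times as wide. With independent reading errors there would be almost no change.

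A reader might go further and infer that the agreement estimate is biased or that the study's main conclusions are at risk. Neither follows. Only precision is affected, the primary aims concern feasibility, safety, tolerability and image quality, and the accuracy comparison has no preplanned test. Severity is minor to moderate, and rests on the stated use of these data to design later trials. The missing weighting and lost location of the count kappa are a supporting point.

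**What to change.** In D.2:

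- Report location-matched segment agreement and segment kappa with patient-clustered 95% intervals: a patient-level t interval for the rate, or a bootstrap that resamples patients for either. Apply the same to any R pooled over segments, and say whether R is pooled or per position.
- Describe 510 as a maximum number of clustered observations from at most 30 patients. Report the evaluable segments per patient and the observed ICC, which later trials will need.
- If the per-patient count comparison is kept, use a weighted kappa with stated weights, or an ICC.
- While editing, define the CT grade bins so that every segment, including those near normal, has one grade.

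The cost is a few sentences and modest programming, with no new data. The downside is wider intervals that are themselves approximate with 30 or fewer patients. In simulation with 30 patients, the patient-level t interval covered 94% to 95% and the percentile cluster bootstrap 93% to 94%. If clustering by patient was already intended, one sentence settles the main point.

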Since we expect to be underpowered to prove that CT perfusion is noninferior to SPECT and/or MRI stress perfusion, we will not do any preplanned statistical comparison of the accuracy for diagnosing significant CAD between CT perfusion and SPECT/MRI stress perfusion. Because all patients will not have invasive angiography, we cannot do analysis for sensitivity or specificity for detection of CAD against this gold standard. Furthermore, we believe that SPECT is an imperfect gold standard against which to judge CT (i.e., SPECT has well known problems with specificity and to a lesser extent sensitivity). However, we will present the comparison of findings with each modality on a per-patient and per-segment basis so that they can be used to help plan subsequent larger, head to head studies that are powered to compare the accuracy of each modality.

B. BACKGROUND AND SIGNIFICANCE

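### Neither statistic named in D.2 for CT versus SPECT/MRI perfusion measures segment-level agreement, and none is named for the segment-level binary analysis planned first

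*Combined protocol and SAP*

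**What the plan says.** Section D.2 (Statistical Methods / Sample Size Justification) sets out three steps for CT perfusion against SPECT or MRI stress perfusion, on the 17-segment model and with at most 510 segments from 30 patients.

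1. A segment-level step: "We will first perform a binary analysis where each segment is classified as either normal or abnormal". No agreement statistic is attached to it.
2. A per-patient step that applies "If feasible based on the number of patients with SPECT/MRI stress perfusion scans". If the condition is met, "we will compare the number of abnormal segments in each patient by each methodology using a kappa statistic". D.2 gives no number for feasibility and does not say whether the kappa is weighted.
3. A severity step on two 1–4 grades. The CT grade is defined "with each segment graded as 1, 2, 3 or > 4 standard deviations from the norm". The analysis is: "We will then perform linear regression (Pearson's correlation) to derive R values for CT perfusion versus SPECT/MRI stress perfusion imaging perfusion grade for each segment". Only R is to be derived; no slope, intercept, mean difference or ordinal agreement measure is named.

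Section A (Specific Aims) adds that "we will present the comparison of findings with each modality on a per-patient and per-segment basis", to help plan larger studies, and states that no statistical comparison of diagnostic accuracy is preplanned.

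**The concern.** A perfusion comparison has to show whether the two methods call the same segments abnormal, and whether they grade them alike. The named statistics answer other questions.

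- A count of abnormal segments discards location before kappa is computed. Three anterior segments on CT and three inferior segments on SPECT count as full agreement. If the kappa is unweighted, counts of 3 and 4 disagree as completely as 0 and 17.
- Pearson's R measures linear association. A constant offset or change of scale between CT and comparator grades leaves it unchanged. D.2 itself notes that defect severity has not been defined for CT, so a systematic grading difference is plausible.

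The output is meant to inform the design of later accuracy trials. A designer who took either figure as agreement could be misled about how often CT and the comparator match, and in which direction they differ.

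**Working it through.** **Inputs from the documents.** 30 patients, 17 segments each, grades 1–4. The plan's own maximum reproduces: 30 × 17 = 510. D.2 gives no expected kappa, R, count distribution or grade mix, so those below are assumptions for illustration.

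**Formulas.** Kappa = (Po − Pe)/(1 − Pe), with Po observed and Pe chance agreement. Quadratic-weighted kappa = 1 − (mean observed squared difference)/(mean squared difference expected by chance).

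**Count kappa.** Assumed comparator counts: 0 in 12 patients, 2 in 5, 3 in 5, 4 in 5, 5 in 3. That makes 10 + 15 + 20 + 15 = 60 abnormal segments in 18 patients.

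*Example 1: CT has the same count in each patient, with no segment shared.*
- Counts are identical, so count kappa = 1.00. This does not depend on the count mix.
- Segments: Po = (510 − 120)/510 = 0.7647; Pe = (60² + 450²)/510² = 0.7924. Segment kappa = (0.7647 − 0.7924)/(1 − 0.7924) = -0.13.

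*Example 2: CT marks the same segments plus one more in each of the 18 abnormal patients (78 in all).*
- Unweighted count kappa: Po = 12/30 = 0.400; Pe = (12×12 + 5×5 + 5×5 + 3×5)/900 = 209/900 = 0.232. Kappa = 0.168/0.768 = 0.22.
- Quadratic-weighted count kappa: observed 18/30 = 0.60. The count means are 2.0 and 2.6 and the variances 3.333 and 5.173, so expected = 3.333 + 5.173 + 0.6² = 8.867. Kappa = 1 − 0.60/8.867 = 0.93.
- Segments: Po = 492/510 = 0.9647; Pe = (60×78 + 450×432)/510² = 0.7654. Kappa = 0.1993/0.2346 = 0.85.

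**Pearson's R on grades.**

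*Example 3: comparator uses grades 1–3 only; CT is one grade higher throughout.* R = 1.00 and exact agreement is 0%, whatever the mix. With an assumed mix of 70/20/10%, each variance is 0.44 and the mean difference is 1, so quadratic-weighted kappa = 1 − 1/(0.44 + 0.44 + 1) = 0.47.

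*Example 4: all four grades used (assumed 60/20/10/10%); CT one grade higher, capped at 4.* Variances are 1.01 and 0.64, covariance 0.78. R = 0.78/√(1.01 × 0.64) = 0.97. Exact agreement is 10%, and those are only the segments already at 4. Mean difference is 0.9.

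*Example 5: CT over-grades only abnormal segments (2→3, 3→4, 4→4; assumed 450 segments at grade 1 and 20 at each other grade).* Centred sums of squares are 1030 − 630²/510 = 251.8 and 1270 − 670²/510 = 389.8; the cross-product is 1130 − 630×670/510 = 302.4. R = 302.4/√(251.8 × 389.8) = 0.965. If grade 2 or above is abnormal, count kappa is 1.00. Yet only 20 of the 60 abnormal segments (33%) are graded alike, with a mean difference among them of 40/60 = 0.67 grade. The pooled quadratic-weighted kappa is itself high here: 1 − (40/510)/[(251.8 + 389.8)/510 + (40/510)²] = 0.94. The cross-table and the mean difference expose the over-grading.

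**Limit on R = 1.** Enumerating the linear maps between grade sets shows that R of exactly 1 with unequal grades requires a comparator that leaves at least one grade unused. If all four are used, R = 1 forces identical grades.

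**The case against.** A reader might go further and infer that both statistics can read perfect while the modalities disagree, so that the planned comparison cannot show agreement. The documents do not support that.

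- **The comparison is wider than two statistics.** D.2 puts the segment-level binary analysis first, and section A promises per-segment findings. Cross-tabulated, those paired calls show agreement by location directly. This stands; the gap is that no statistic or interval is named for them.
- **The two statistics partly check each other.** In Example 1, R on the 510 paired calls is -0.13 and exposes the mislocation. In Example 3, if grade 2 or above is abnormal, every CT segment is abnormal and count kappa is 0.00. With a pooled R of 1, equal counts and a grade cut-off for abnormal, none of 11,862 enumerated small cases hid a location disagreement. Both statistics at exactly 1.00 needs a special construction. One is comparator grades {1, 2} against CT grades {1, 4}, where the binary calls still agree perfectly; another is a separate R for each segment position. The cross-check itself needs a pooled R and a grade-based abnormal call. D.2 settles neither, and the count kappa may not be run at all.
- **Unweighted kappa is not stated.** A charge that the plan penalises near-identical reads rests on 0.22; quadratic weights give 0.93. What stands is that the choice is left open.
- **Little hangs on it.** The comparison is secondary and declared unpowered, and no decision rule uses either figure. That limits the consequence. Low power widens intervals, but it does not make a count or a correlation an agreement measure.

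**Conclusion.** The point holds in this form. Neither named statistic measures segment-level agreement, and the analysis that could do so has none named. That count kappa ignores location, and that R ignores shift and scale, are properties of the statistics and need no assumption. The sizes are illustrative: they rest on assumed count and grade mixes, and exact R = 1.00 under a shift also needs a comparator that does not use all four grades. With all four in use, R of about 0.96–0.97 can still accompany exact agreement in only a minority of the shifted segments. The planned per-segment presentation partly mitigates the problem. The change is worth making because the stated use is planning later trials, but it does not touch the feasibility, safety or tolerability aims.

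**What to change.** In D.2:

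- Attach kappa to the paired segment-by-segment normal/abnormal calls, and repeat it per vascular territory. Give intervals that allow for up to 17 segments from one patient, for example by a bootstrap that resamples patients.
- If counts are kept, replace their kappa with the mean CT-minus-comparator difference and limits of agreement.
- For grades, report the 4×4 cross-table, a weighted kappa with its weights stated, and the mean grade difference, also among segments abnormal on the comparator, since a pooled coefficient is dominated by normal segments. Keep R as descriptive only, and say whether it is pooled or computed per segment position.
- State whether the normal/abnormal call is a separate visual reading or a cut-off on the grade.

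The cost is protocol wording and slightly more analysis on the same data and readings. The reported agreement may look less favourable than R alone.

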Dynamic CT MPI data are reconstructed with a section thickness of 3 mm and a 2 mm increment with a medium smooth convoluted kernel (B30). The data are processed with the volume perfusion CT body application software and workstation (Siemens). After motion correction and 4D noise reduction, a double arterial input function is defined by placement of ROIs in the descending aorta in the cranial and caudal regions of the covered volume. After a volume of interest is manually defined around the left ventricle, the left ventricular myocardium is automatically segmented. A dedicated parametric deconvolution algorithm based on a two-compartment model of intravascular and extravascular space is used to derive myocardial blood flow and the volume transfer constant (k^{trans}) from the time-attenuation curves for each voxel.²³

Quantitative Measures of Myocardial Blood Flow from CT:

CT perfusion images will be analyzed on a dedicated console using commercially available software (Syngo Volume Perfusion™) as previously described.²⁴ Evidence of ischemia will be determined initially by visual comparison of rest and stress CT perfusion scans. Perfusion defects will be visually rated as reversible (only present at stress), fixed (present at both rest and stress) and mixed (more pronounced at stress, partly reversible at rest). Quantitative analysis of myocardial perfusion will be performed and mean blood volume (MBV), mean blood flow (MBF), and mean transit time (MTT) of each myocardial segment will be recorded. Readers will be blinded to the results of SPECT or invasive angiography examinations. The values obtained will be compared to historical published values for each parameter (MBF, MBV, and MTT) obtained using older generation CT perfusion protocols, MRI perfusion, or dynamic perfusion scanning.

Analysis of SPECT images:

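### Continuous segmental CT blood flow is recorded, but D.2 names no analysis of it against the patient's own SPECT/MRI result; the severity comparison appears to use a four-level grade with undefined gaps

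*Combined protocol and SAP*

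**What the plan says.** Section D.1 (Quantitative Measures of Myocardial Blood Flow from CT) states that "mean blood volume (MBV), mean blood flow (MBF), and mean transit time (MTT) of each myocardial segment will be recorded". The use it gives for those numbers is external: "The values obtained will be compared to historical published values for each parameter". It also says that "Evidence of ischemia will be determined initially by visual comparison of rest and stress CT perfusion scans".

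Section D.2 lists three comparisons of CT with SPECT/MRI:

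- **Binary, per segment.** "We will first perform a binary analysis where each segment is classified as either normal or abnormal". The reason given is that the relative severity of defects is not yet defined for CT. No flow cut-off is stated.
- **Count per patient.** If numbers allow, "we will compare the number of abnormal segments in each patient by each methodology using a kappa statistic". The count derives from the binary call.
- **Severity.** SPECT/MRI is graded 1–4. CT gets a similar 1–4 scale from absolute perfusion in ml/100 ml/min, "with each segment graded as 1, 2, 3 or > 4 standard deviations from the norm". Linear regression and Pearson's R follow.

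D.2 assumes 30 patients and at most 510 segments. Section D.1 and the enrollment table in E.1.a give 100 subjects.

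**The concern.** Nowhere does the plan say that the measured flow will be set against the patient's own comparator result. The reason given for the binary step does not require this omission: a flow value in ml/100 ml/min needs no severity definition, and only the comparator has to be ordinal.

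Sections A and D.2 say that these comparisons are meant to help plan later, adequately powered studies. Grading the CT value first makes the estimates less precise than the recorded data allow, and R then depends partly on where the bin edges fall. The CT scale is also incomplete as written. A segment 3.5 SD from the norm has no grade, and a segment within 1 SD has none explicitly. Two analysts could therefore build different scales from the same text.

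**Working it through.** **The plan's own figure.** 30 patients × 17 segments = 510, as D.2 states. The plan gives no effect size, power or information-loss figure to reproduce. The rest is conditional on assumptions.

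**Information lost by four grades.** Assume the flow deficit, in SD units of the norm, is normal with mean m and SD s. Assume cuts at 1, 2 and 3 SD and scores 0 to 3. With φ the standard normal density, the information kept is the squared correlation between grade and value:

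efficiency = [Σ φ((c − m)/s)]² / Var(grade), over c = 1, 2, 3.

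- m = 0, s = 1 (segments distributed as the norm): the sum is 0.2420 + 0.0540 + 0.0044 = 0.3004 and the variance is 0.2003. Efficiency is 0.0902/0.2003 = 0.45, so the loss is 55%. Some 84% of segments fall below the first cut.
- m = 0.5, s = 1.25: loss 33%.
- m = 1, s = 1: the sum is 0.3989 + 0.2420 + 0.0540 = 0.6949 and the variance is 0.6254. Efficiency is 0.77, so the loss is 23%.
- m = 2, s = 1.5: loss 14.5%.
- m = 2, s = 1: the sum is 0.2420 + 0.3989 + 0.2420 = 0.8829 and the variance is 0.8846. Efficiency is 0.88, so the loss is 12%.

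**Effect on power.** Simulation assumptions: 30 × 17 segments, half the patients with any abnormal segment, 20% of segments abnormal on the comparator, within-patient correlation 0.3, unaffected segments centred on the norm, a patient-clustered test at 0.05 and 1,500 replicates.

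| MBF fall per comparator grade | Continuous MBF | Four CT grades |
|---|---|---|
| 0.15 SD | 58% | 30% |
| 0.2 SD | 77% | 53% |
| 0.3 SD | 97% | 86% |
| 0.5 SD | 100% | 100% |

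At 0.3 SD the mean test statistic is 4.49 continuous and 3.17 graded. The ratio is 0.71, and its square is about 0.5, in line with the unfavourable case above.

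**Sensitivity to the norm.** If all segments sit 1 SD below the norm, power at 0.2 SD is about 78% continuous and 72% graded; at 0.3 SD it is 97% and 96%. Across repeat runs the loss at 0.15–0.3 SD was between about 1 and 10 points.

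**Effect on R.** Graded versus continuous R was 0.14 versus 0.17 at 0.2 SD per grade, and 0.64 versus 0.57 at 0.8 SD. The bins can move R either way.

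**Clustering.** With design effect 1 + 16 × ICC, 510 segments are worth 510/2.6 = 196 independent ones at an ICC of 0.1, and 510/9 = 57 at 0.5. D.2 states no adjustment for this, so the model needs the patient as a cluster.

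**The case against.** A reader might infer that every CT versus SPECT/MRI analysis first cuts measured flow and throws away about half the information. The documents do not support that.

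- The binary call, and the kappa built on it, may be a visual read. D.1 determines ischemia visually first, and D.2 gives no flow cut-off.
- The Pearson sentence names CT perfusion against the SPECT/MRI grade. It could mean the flow value itself, although it directly follows the definition of the CT grades, which makes grade against grade the likelier reading.
- About half is the unfavourable case for four grades. Nor is it a ceiling for a binary cut, if flow were cut: the loss is then 36% at an even split, 50% with about 21% of segments abnormal and 87% with 2.3% abnormal.

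The power loss is also confined to weak relations. A fall of 0.15–0.3 SD per grade means that comparator grades 1 and 4 differ by only 0.45–0.9 SD (three steps), and at 0.5 SD per grade four-grade power is unaffected. Power is in any case a limited yardstick, because Section A plans no formal accuracy comparison with SPECT/MRI and D.2 says the study is not powered for accuracy.

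Finally, D.2 wants these data to help design accuracy trials, and those need paired normal/abnormal calls. The binary table therefore has a purpose of its own and should not be demoted.

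All of this stands, and it limits the size and reach of the point. It does not supply an analysis of continuous flow against the patient's comparator, nor does it fill the gaps in the grade definition.

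**Conclusion.** The point holds as an omission in a secondary analysis. Segmental flow is recorded, no named analysis sets the continuous value against the patient's own SPECT/MRI result, and the CT severity scale has undefined ranges.

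The loss from grading is roughly 12–23% when segments average 1–2 SD below the norm and about 55% when nearly all are normal. These figures rest on normality and on cuts at 1, 2 and 3 SD, neither of which the plan states. The power figures rest in addition on the simulated prevalence, correlation and sample of 30.

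What is at stake is the precision and interpretability of planning estimates. The primary aims of feasibility, safety, tolerability and image quality are untouched. The 30 patients in D.2 must be reconciled with the enrollment of 100, since every route through prior SPECT or MRI leads to stress CT. The proportionate loss per patient applies at either number; the power figures do not.

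**What to change.** In D.2:

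1. Make continuous segmental MBF (ml/100 ml/min) the CT variable in the severity comparison. Model it on SPECT/MRI grade (1–4) with a patient random effect, or use a Spearman correlation with a patient-level bootstrap. Report the MBF difference per comparator grade with its 95% CI.
2. Keep the binary comparison as planned, and state whether the call is a visual read or a flow cut-off and, if the latter, which.
3. Show the 1–4 CT grades as a supplementary display, with boundaries that cover every value, including below 1 SD and between 3 and 4 SD.
4. Reconcile the 30 patients with the enrollment of 100.

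The cost is wording and one extra model. MBF per segment is already collected, so no new scans, reads or patients are needed. The small downside is a severity result in flow units rather than on a matched 1–4 scale, which the supplementary display covers.
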